OAS-M: The OAS-M is a 25-item clinician-administered, semi-structured interview with nine subscales^{45, 47}. It was designed to evaluate various manifestations of aggressive behaviors in outpatients, including the severity, type, and frequency of aggressive behavior. The scale assesses three overall domains: Aggression (Verbal Aggression, Aggression Against Objects, Aggression Against Others, and Aggression Against Self), Irritability (Global Irritability and Subjective Irritability), and Suicidality (Suicidal Tendencies, Intent of Attempt, and Lethality of Attempt). Only the Aggression and Irritability subscales will be used in the current study. The two Irritability subscales are rated on Likert-type scales from 0 = none at all to 5 = extreme. The Aggression scale uses a different format in which each specific behavior is scored separately by frequency and then multiplied by assigned weights. For each Aggression subscale, seven specific behaviors are listed in order of severity and then weighted by their respective rank. The weighted frequencies are summed to form each subscale score. Subscale scores are then multiplied by their own assigned weight: Verbal Aggression by 1, Aggression Against Objects by 2, and Aggression Against Others and Self each by 3. Weighted subscales are added to obtain a final scale score for Aggression. Evidence for inter-rater and test-retest reliability has been documented for the OAS-M, with intraclass correlations (ICCs) of .91 and greater for inter-rater, and ICCs of .46 to .54 for test-retest reliability, and the OAS-M has demonstrated sensitivity to pharmacotherapy-induced changes in aggression^{47, 48}. The time frame of the OAS-M is restricted to the past week. The OAS-M will be administered by interviewers blinded to treatment condition.

Anger Consequences Scale (ACQ): The ACQ is a brief self-report measure developed to assess the frequency of negative anger-related behavioral consequences. Internal consistencies of .75 to .91 were reported on the original 42 item version; the revised version shortened the measure to 33 items based on factor analysis⁴⁹. This scale includes items not covered by the other anger measures, including for example, trouble with the law, driving recklessly, getting into an accident, damaging relationships, etc.

Dimensions of Anger Response (DAR): The DAR, developed by Novaco⁵⁰ is a 7-item self-report measure of anger reactions. A more recent report on the psychometrics of the DAR showed it to be unidimensional, reliable, and sensitive to change over time^{50, 51}. The DAR will be administered at each session.

D. 3. Collateral Assessments

Data from collaterals can provide an important additional perspective on treatment outcome. We will ask participants if they are willing to have a significant other complete

anger outcome measures for the purpose of providing an additional perspective on amount and types of change following treatment. For each participant who agrees, we will ask him or her to identify the person or persons with whom they spend the most time, and/or have sufficient interactions to be familiar with the participant's typical behavior. A minimum of 5 hours of contact a week will be required to qualify as a collateral reporter. If there are multiple possible candidates, we will ask the participant to identify the one who they believe would be the best able to provide a valid assessment of their anger. Participants may take up to two days to consider the request and to discuss with the potential collateral. If the participant agrees, s/he will be asked for permission to contact the nominated individual as part of the consent process. Although encouraged, identification of collaterals will not be required for inclusion in the study. Collaterals will be fully informed of the study requirements and if they are willing to participate, will be asked to sign informed consent. Collaterals will also be provided with the Notice of VHA Privacy Practices. They will be asked to complete the STAXI-II (excluding the state anger scale), the Sheehan Disability Scale, and the Overt Aggression Scale interview at pre- and posttreatment. These measures will be adapted from first to third person for this purpose. We will record demographic information, the nature of the relationship (e.g. spouse, family member, friend) and the average number of hours of contact per week with the participant. At post-treatment, we will also administer a collateral version of the Patient Satisfaction form.

D. 4. Secondary Outcome Measures: Functioning and Quality of Life

Longitudinal Interval Follow-Up Evaluation: Psychosocial functioning scales from the clinician administered Longitudinal Interval Follow-up Evaluation⁵² will provide assessment of functioning in areas of work (employment, household, or student), familial and nonfamilial interpersonal relationships, recreation, and global social adjustment on separate 6 to 8-point scales. Ratings will be based on the past month. The psychosocial functioning ratings have been found to be of generally high reliability^{52, 53}.

Outcomes Questionnaire: Functioning will also be assessed by the self-report Outcomes Questionnaire (OQ) which was developed as a psychotherapy outcome measure⁵⁴. The OQ includes three subscales: symptom distress, interpersonal relations, and social role functioning. Test-retest coefficients in the mid .70s and .80s and internal consistency in the low .90s provide evidence for reliability. Concurrent validity has been demonstrated in relation to other measures, the OQ has been shown to be fairly stable in untreated individuals and sensitive to change in those individuals in treatment⁵⁵.

World Health Organization Quality of Life (WHOQOL-BREF): The World Health Organization Quality of Life (WHOQOL-BREF), is 26 item self-report measure used to assess quality of life in multiple domains (i.e., physical, psychological, social, and environment). Psychometric properties suggest that the measure is valid and reliable across cultures and nations⁵⁶.

D. 5. Mediators of Outcome

Novaco Anger Scale (NAS): The three subscales of the NAS (cognitive, arousal, and

behavioral) will be examined as possible mediators of CBI treatment outcome. The revised version of these scales includes 48 items measuring impairment in the three components of Novaco's model^{57,58}. As described further below, the intervention in the current study, adapted from Novaco's stress inoculation anger control treatment, includes strategies to address each of these components. The published manual for the NAS-PI^{57,58} reports findings of high levels of internal consistency across a number of normal and psychiatric samples. Of particular relevance to the population to be addressed in this study is the data provided by Chemtob and colleagues on 114 Vietnam veterans which yielded alpha coefficients of 0.97 and 0.96 for the NAS and PI, respectively²⁵.

D. 6. Additional measures

Treatment Satisfaction: a brief 4 item measure adapted from the Treatment Satisfaction Form used in the NIMH Treatment of Depression Collaborative Research Program will be used to assess satisfaction with treatment.

Treatment Utilization: The Longitudinal Interval Follow-Up Assessment (LIFE) treatment section provides continuous recording of mental health and medical treatments⁵². For the latter, number of hospitalizations, days spent in hospital, and number of outpatient visits for non-mental health medical treatments are recorded for the time period covered. Types and amounts of all mental health contacts, including inpatient and outpatient treatment, are recorded on a monthly basis. All psychiatric medications, including dosages are recorded on a weekly basis (see Appendix 4 for list of medications). We will also assess all prescribed non-psychiatric medications, over the counter medications (including caffeine), and herbal and other supplements taken for any reason.

A baseline version (LIFE-Base) assesses mental health treatment received prior to entering the study. We will adapt the LIFE-Base to indicate whether prior treatment occurred before, during, or after deployment, and also to assess whether prior treatment focused specifically on anger or PTSD.

D. 7. Schedule of Assessments

The schedule of assessments is shown in Table 1. The CAPS and the SCID will be administered during the screening process prior to randomization to ensure that only eligible participants are entered into the study. Only eligible participants will complete the full CAPS and SCID and other pre-treatment measures. Assessments will be conducted at pre-treatment, during treatment (after sessions 4 and 8), end of treatment (week 12), and at three and six months following completion of treatment. We estimate that completion of the SCID and the CAPS will take 2 hours on average, and that the remaining pre-treatment measures will take about 2 ½ hours. The pre-treatment assessment will be conducted in 2 sessions. Mid-treatment assessments should take about 45 minutes. We estimate that post-treatment and follow-up assessments will take about 2 ½ hours on average.

We will aim to complete the post-treatment and follow-up assessments in a single

session, providing breaks if needed. If necessary due to participant burden, we will schedule a second assessment session. We will prioritize the order of measures administered to ensure that in all cases the anger outcome measures (OAS-M, STAXI-2, and ACQ), and the Outcomes Questionnaire are completed. Telephone assessments will be used if participants are unable to come in for assessments. Every attempt will be made to perform post-treatment and follow-up assessments within one week of their scheduled date.

Table 1. Schedule of Assessments

Domain	Screening	Pre-Tx	Sessions 4 and 8	Post-Tx	Follow-up (3 and 6 months)
Inclusion/exclusion Criteria					
SCID	X				
CAPS	X			X	X
Sample Characterization					
SNAP-2		X			
CTQ		X			
Combat Exposure		X			
BSI		X	X	X	X
BAM (Use subscale)		X			X
Anger					
OAS-M*		X	X	X	X
STAXI-2*		X	X	X	X
ACQ*		X		X	X
DAR (weekly)					
Function/QOL					
LIFE psychosoc		X		X	X
OQ		X		X	X
Disability Scale		X		X	X
WHOQOL-BREF		X		X	X
Mediators					
NAS arousal		X	X	X	
NAS cognitive		X	X	X	
NAS behavioral		X	X	X	
Other Measures					
Tx Satisfaction				X	
LIFE Tx section	X			X	X

Clinician administered interviews are in italics. ACQ = Anger Consequences Scale; BAM = Brief Addiction Monitor; BSI = Brief Symptom Inventory; CTQ = Childhood Trauma Questionnaire; DAR = Dimensions of Anger Scale; NAS = Novaco Anger Scale; OAS-M = Overt Aggression Scale Modified; OQ = Outcomes Questionnaire; SNAP-2 = Schedule for Nonadaptive and Adaptive Personality-2nd Edition; STAXI-2 = State Trait Anger Inventory-2; WHOQOL-BREF = The World Health Organization Quality of Life

*Collateral assessments will be administered at pre- and post-treatment

D. 8. *Blinding of Assessments*

All interviewers will be blind to participants' treatment condition. Each of the outcome domains (anger, functioning/quality of life) includes one blinded interview. Prior to the outcome assessments, the interviewer will remind each participant not to reveal his treatment condition. At the post-treatment and follow-up assessments, interviewers will complete questions including whether they think the blind was broken, and to which treatment condition they think the participant was assigned.

D. 9. *Standardization of Assessments*

Interviewer qualifications will include masters or doctoral level training in psychology or social work, or bachelor's level training combined with at least 2 years of prior experience using structured interviews. Research study staff will provide training on the SCID and the CAPS. This research study staff member has formal training and experience training others on these interviews. [name] will conduct training on the OAS-M. Interviewers will conduct practice interviews and receive feedback from Research Study staff and [name] until judged to be calibrated to an acceptable standard of administration.

All of the clinical interviews (CAPS, SCID and OAS-M) will be recorded. Ten percent of each of the interviews will be randomly selected on an ongoing basis to monitor the reliability of the interview process. Research study staff will listen to the recorded interviews and provide feedback to interviewers in biweekly meetings to maintain reliability. Interviewer ratings will be compared with research study staff's ratings and any discrepancies in ratings will be discussed.

D. 10. *Procedures to Enhance Completion of Assessment Protocols*

A number of procedures will be used to minimize the likelihood that participants will fail to complete the schedule of assessments. Self-report measures will be completed at the time of the assessment and reviewed for completeness before the participant leaves. We will monitor carefully for fatigue, and encourage breaks if needed. We will try to schedule assessments on the same day as treatment sessions. Participants will be compensated for all assessments.

Permission will be requested at the time of informed consent to obtain the name and phone number of a close relative, friend, or other person who is likely to maintain contact with the participant, and to contact that person if attempts to contact the participant are unsuccessful. Post-treatment and follow-up assessments will be conducted in person at appointments scheduled for this purpose. An appointment for the three-month follow-up assessment will be made at termination of the study intervention, and for the six-month follow-up at the three-month interview. Participants will receive a letter one week prior to the interview and a reminder call a few days prior. Participants who do not have telephones will be contacted by mail and asked to call for an appointment. Five contact attempts will be made before a participant is considered to be unreachable at that time point. Participants who fail to appear for a scheduled assessment will be contacted by phone, or mail when necessary, for rescheduling. If participants move away during their

participation in the study, or are otherwise unavailable for an in-person interview, we will perform follow-up assessments over the telephone to avoid missing data.

D. 11. Compensation

Participants will be compensated for the time required to complete all assessments. They will be paid \$100 for the pre-treatment baseline assessment and \$60 for the subsequent post-treatment and follow-up assessment periods.

Participants who screen out on the SCID or CAPS or who do not complete the full baseline assessment will be paid \$40 (for partial assessment). Mid treatment assessments (after sessions 4 and 8) will be compensated at \$25. Collaterals will be compensated \$25 for the pre- and post-treatment assessments. Participants can receive their compensation in the form of an electronic funds transfer or gift card. Collaterals will be compensated with gift cards.

E. Treatment

E. 1. Assignment

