(1) To investigate the efficacy of CBI on primary measures of anger treatment outcome. We hypothesize that:

- a) Compared to SI, CBI will be associated with significantly larger reductions in anger and aggressive behaviors at post-treatment and at 3 and 6 month follow-ups.

(2) To investigate the efficacy of CBI on secondary measures of anger treatment outcome. We hypothesize that:

- a) Compared to SI, CBI will be associated with significantly more improvement in social functioning, occupational functioning, quality of life, and PTSD symptoms at post-treatment and at 3 and 6 month follow-ups.

(3) To examine mechanisms of action of CBI. We hypothesize that:

- a) Change in arousal, cognitive, and behavioral domains of anger will mediate outcome for anger and functioning in the CBI condition.

(4) To examine the effectiveness of CBI for those with and without PTSD. We hypothesize that:

- a) CBI will be superior to SI on primary and secondary outcome measures (aims 1 and 2) for those with and without PTSD.

2. Background, Significance, and Rationale

Anger Problems in Military Personnel and Veterans: Poorly controlled anger is a common

problem with often devastating effects in veterans who have served in a warzone. As early as World War II, anger and aggression were identified as common responses to combat stress ^{1, 2}, and the association between combat experience and symptoms of anger and hostility has repeatedly been demonstrated in empirical research ^{3, 4, 5}. Findings from the National Vietnam Veterans Readjustment Survey⁴ showed that Vietnam veterans exposed to high levels of war stress expressed higher levels of hostility and committed more violent acts compared to Vietnam era (non theatre) veterans, civilians, and theatre veterans exposed to lower levels of war stress. Excessive anger and difficulty managing anger were also shown to increase risk for divorce, domestic violence, job loss and instability, and other serious impairments in family, social, and occupational functioning ⁴.

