effect over time, though there will also be a test for the time by treatment interaction. Significant time by treatment interactions will be followed up by post hoc tests at specific assessment points by calculating simple intercepts, simple slopes, and regions of significance. Relevant covariates will be included to adjust for any imbalances across treatment conditions.

Missing data will be dealt with as follows. HLM analyses can include cases with some time points missing. In the primary analysis, we will include all cases with at least 3 of the 5 outcome time points (4 & 8 weeks, posttreatment, and 3 & 6 months) non-missing. Then, we will conduct a sensitivity analysis including all randomized participants, in which any missing outcome values will be filled in with baseline scores, which is an extreme assumption. Consistency of results from the two approaches will bolster the credibility of the primary analysis.

The primary dependent variables for aim 1 are the STAXI-2 Anger Expression Index, and the OAS-M Aggression Scale score. Outcome on these measures is assessed at 4 and 8-week points during treatment, at post-treatment, and at 3 and 6 months follow-up assessments. DVs for aim 2 include two LIFE scales (global social and work functioning), the Outcomes Questionnaire total score, the WHOQOL-BREF total score, and the CAPS total score. Outcome on these measures is assessed at post-treatment and 3 and 6-month follow-up assessments.

For aims 1 and 2 the alpha will be set at .025 to account for multiple dependent variables.

Supplementary post-treatment outcome analyses will be conducted using collateral measures (including the STAXI-II, Anger Control Scale and Modified Overt Aggression Interview). We will calculate Pearson correlations of participant and collateral scales as an indication of agreement. If outcome analyses based on collateral measures are consistent with analyses of participant measures, this would bolster the validity of the participant outcome findings. Divergent findings could be due to multiple factors that could influence the validity of the participant and the collateral reports. In this case we will conduct analyses using integrated collateral and participant scores, calculated by averaging the participant and collateral responses to each item.

Aim 3: (Exploratory) Examine hypothesized mechanisms of action of CBI

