Hypothesis: Change in arousal, cognitive, and behavioral domains of anger will mediate outcome for anger and functioning in the CBI condition.

In order to examine the mediating role of arousal, cognition, and behavior (NAS scales), we will use arousal, cognition, and behavior at post-treatment as mediators of the effect of treatment in predicting later anger and functioning at months 3 and 6. Therefore, these mediation tests will be fully prospective, as recommended by Kazdin & Nock⁶⁶, and as exemplified in prior mediational research done by [name]. These analyses will covary for the baseline scores of the mediators. Mediation of treatment effects through NAS scales will be tested using the Sobel test^{69, 70}. Simulation tests indicate that we will have more than 80% power to detect mediation when both paths have small to medium effect sizes⁷¹.

Aim 4: (Exploratory) Examine the effectiveness of CBI for those with and without PTSD. We will test for an interaction between CBI vs. SI and PTSD status by calculating simple slopes. Since we will not have 80% power to test this interaction, we will calculate treatment effect sizes separately for the PTSD and the no-PTSD cases.

G.3. Power Analysis

Power for our repeated-measures design was estimated using methods described by Faes et al.⁷¹. We obtained intervention effect sizes ranging from 0.78 to 1.12 in our pilot study, but given the small sample and the instability of effect sizes derived from pilot studies⁷² we have conservatively based our statistical power analysis for detection of medium effects.

We will use a two-sided alpha level of .025 in the primary and secondary outcome analyses to correct for the number of dependent variables; i.e., each DV will be tested individually with an alpha level of .025, keeping the study-wise alpha at .05. With this alpha level and an estimated 80% follow-up, a sample size of 120 will provide 90% power to detect a medium effect size of .60.

H. Time-Line

We anticipate the following time-line for the study:

Months	
0-6 Hiring, Training, IRB approvals	12-42 Follow-Up (6 month)
6-33 Recruitment	6-43 Data Entry and Management
6-36 Treatment	43-48 Final Data Analyses and Manuscript
9-39 Follow-Up (3 month)	Writing

I. Dissemination and Future Plans

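### Hypothesis 3a places mediation in the CBI condition, but the Aim 3 test names no NAS-by-arm term and so cannot separate a CBI link from one present mainly in SI

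*Combined protocol and SAP*

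**What the plan says.** Section 1 (Purpose, aim 3) and section 4.G.2 (Aim 3) state the same hypothesis: "Change in arousal, cognitive, and behavioral domains of anger will mediate outcome for anger and functioning in the CBI condition". Section 4.D.5 says that the three NAS subscales "will be examined as possible mediators of CBI treatment outcome".

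The method in 4.G.2 takes post-treatment NAS scores "as mediators of the effect of treatment in predicting later anger and functioning at months 3 and 6". On covariates it says "These analyses will covary for the baseline scores of the mediators". On the test it says "Mediation of treatment effects through NAS scales will be tested using the Sobel test". It names no NAS-by-arm term, no slope for each arm and no analysis within CBI. Interactions are named elsewhere in 4.G.2: time by treatment for Aims 1 and 2, and treatment by PTSD status for Aim 4.

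The analysis section labels the aim exploratory: "Aim 3: (Exploratory) Examine hypothesized mechanisms of action of CBI".

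**The concern.** For NAS change to carry outcome in CBI, post-treatment NAS has to predict later outcome among CBI participants. A Sobel product built from one arm effect on NAS and one NAS-to-outcome slope does not check that. The common slope mixes the two arms. A significant product is therefore compatible with a link in both arms, in CBI alone, or in SI alone.

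At stake is the sentence that the trial report will carry about how CBI works. If the slopes differ, a statement about the CBI condition based on the common slope could be too small, too large, or about the wrong arm. The issue is separate from the choice of the Sobel test: a joint-significance test on the same model would share it.

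**Working it through.** **The plan's own figure.** For Aim 3 the plan says "Simulation tests indicate that we will have more than 80% power to detect mediation when both paths have small to medium effect sizes". It gives no path values, N or alpha, so the figure cannot be reproduced. Simulated Sobel power with both standardised paths equal, N = 96 and two-sided .05, is 29% at .26, 47% at .30, 71% at .35 and 85% at .39. More than 80% needs both paths near .38 (near .34 with N = 120). As usually computed, such a figure concerns the common-slope product, so it says nothing about a CBI-arm effect.

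**Inputs from the documents.** N = 120 and 80% follow-up (4.G.3) give 120 × .80 = 96, or 48 per arm if balanced. Tests are two-tailed (4.G.2).

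**Assumed, because the documents do not give them.** Alpha .05 for Aim 3 (.025 is set for Aims 1 and 2 only); 1:1 allocation; baseline-to-post NAS correlation .5; arm effect on NAS a = .3 to .6 SD; the slopes shown below.

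**What the common slope estimates.** Let b_CBI and b_SI be the slopes in each arm, n the arm size and s² the variance of post-treatment NAS left after baseline NAS. The common slope is then approximately

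b_common = (n_CBI·s²_CBI·b_CBI + n_SI·s²_SI·b_SI) / (n_CBI·s²_CBI + n_SI·s²_SI).

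With equal arms and equal s² this is the simple average. The Sobel statistic is z = a·b / √(a²·SE_b² + b²·SE_a²).

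**Estimate against the CBI-arm value (a = .6):**
- Slopes .2 in SI and .4 in CBI: common slope (.2 + .4)/2 = .30, so .6 × .30 = .18. The CBI-arm value is .6 × .4 = .24.
- Slope .5 in CBI only: common slope .25, so .15. The CBI-arm value is .30. In simulation, the 95% interval covers the CBI value in 53% of trials, against 92% with the CBI slope.
- The factor of one half in that case needs equal arms and equal s². With a CBI residual SD 1.5 times that of SI, the share kept is 2.25/3.25 = 69%. With the ratio reversed it is .444/1.444 = 31% (32% in simulation).

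**How often an SI-only link of .5 is declared mediation (simulation, 48 per arm):**

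| Arm effect on NAS | Common slope |
|---|---|
| .3 SD | 7% |
| .4 SD | 14% |
| .6 SD | about 30% |

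At .6 SD the same test with the CBI slope rejects in 2%. With no link in either arm the common-slope test also rejects in about 2%. The problem therefore needs both a real arm effect on NAS and a link in SI.

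**Equal slopes (.3 in each arm, a = .6).** Both estimates are unbiased. The CBI-arm SE is larger: .110 against .090 in one set of runs (ratio 1.22) and .114 against .092 in another (ratio 1.24). Power falls from about 44% to about 25%.

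**Power of the interaction test itself.** About 65% for a slope difference of .5 and about 15% for a difference of .2.

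**The case against.** The case for leaving the plan alone has five parts.

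1. **The model is not written out.** A reader might infer that the plan commits to one slope for both arms. The documents do not say so. They are silent on the term, and the common slope is only the natural reading of a Sobel test described without an interaction. This stands, and it is why the point concerns specification and wording.

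2. **The hypothesis may be loosely worded.** Aim 3 is headed as mechanisms of action of CBI, and the method speaks of treatment effects. The phrase locating mediation in the CBI condition may only mean how CBI outperforms SI, which a two-arm test addresses. This is a fair reading. If it is the intended one, 3a should say so.

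3. **The CBI-arm product is also a choice.** It still multiplies by the CBI-versus-SI contrast on NAS, so it is not mediation wholly within CBI. Products with either arm's slope are recognised indirect effects, and the common-slope product is roughly their average. The 30% rate is an error only for a claim about CBI.

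4. **Nothing shows that the slopes differ.** Section 4.E.3 describes SI as supportive, with problem solving and without cognitive or behavioural strategies. That bears on how far NAS moves in each arm more than on how strongly NAS predicts outcome. A reader might infer that a false mechanism claim is likely; the documents do not support that. Slopes of exactly zero in one arm are limiting cases.

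5. **The remedy costs precision.** A rule allowing mediation to be claimed only from the CBI-arm estimate would cut power when slopes are equal. This stands, so that rule is not proposed.

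What remains is that hypothesis and described test do not match as written, and that the assumption reconciling them, equal slopes, is neither stated nor examined.

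**Conclusion.** The point holds as a minor one. On the common-slope reading, the Aim 3 test supports mediation of the CBI-versus-SI effect if the NAS-to-outcome slopes are equal. It does not by itself support a statement about the CBI condition. Under moderate heterogeneity the estimate falls short of the CBI-arm value by a quarter (.18 against .24: .06/.24 = 25%); with a link in CBI only, by about half. The chance of declaring mediation from an SI-only link of .5 runs from 7% to about 30% as the arm effect on NAS goes from .3 to .6 SD. These figures rest on 48 per arm, alpha .05 and the assumed slopes and correlation. The halving also rests on equal arms and equal residual NAS variance.

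A reader might go further and conclude that the planned mediation test is invalid. It is not: with equal slopes it is unbiased and more powerful. Because Aim 3 is exploratory, the confirmatory conclusions of the trial are untouched.

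**What to change.** Keep the planned estimate and write out its outcome model. As a prespecified companion, add a NAS-by-arm term to each Aim 3 outcome model. Report the NAS-to-outcome slope in each arm, the interaction with its confidence interval, and the indirect effect that uses the CBI slope.

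Word the conclusions to match. The common-slope result supports mediation of the CBI-versus-SI effect, assuming equal slopes. Any statement about the CBI condition should be accompanied by the CBI-arm estimate and its confidence interval. The alternative is to reword 3a as mediation of the CBI-versus-SI effect.

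The cost is one extra term and a few reported estimates per model, repeated over the three NAS scales and the chosen outcomes, with no new data. The CBI-arm estimate is less precise (SE about 22% to 24% larger with equal slopes). The interaction test has low power for modest slope differences, so a non-significant interaction should not be read as evidence that the slopes are equal.
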